Protocol Number: 20220254

National Clinical Trial (NCT) Identified Number: NCT06938230

Principal Investigators: [name], DO & [name]

Grant Title: Maximizing Child Health and Learning Potential: How to Promote A School Culture of Safety in the era of COVID-19

Grant Number: 1OT2HD108111-01

Funded by: National Institutes of Health (NIH) - Eunice Kennedy Shriver National Institute of Child Health and Human Development (NICHD)

Version Date: April 24, 2025

1) Protocol Title

Promoting A School Culture of Safety in the era of COVID-19: Assessing Feasibility and Impact of a Health Education Initiative

2) Objectives*

The primary purpose of this study is to evaluate the feasibility and impact of a COVID-19 health initiative in at-risk urban school settings. This protocol is comprised of 3 components:

- **Part 1A:** Evaluating the feasibility and acceptability of a health education initiative in school health settings.
- **Part 1B:** Assessing COVID-19 knowledge and experience among caregivers of students in at-risk urban school settings post-intervention.
- **Part 1C:** Evaluating the impact of the health education initiative on vaccination rates and other health behaviors 3 months following the intervention.

The second purpose of this study is to compare COVID-19 knowledge, experiences, and health behaviors between participants who received the health initiative and those who did not (controls), through:

- **Part 2A:** Comparing COVID-19 knowledge, experience, and health behaviors of participants in the health education initiative to controls, immediately following the initiative.
- **Part 2B:** Comparing COVID-19 knowledge, experience, and health behaviors of participants in the health education initiative to controls, three months after the initiative.

3) Background*

Covid-19 has infected over 31 million individuals in the United States (CDC, 2021), over 3.54 million of whom were children (AAP, 2021). The pandemic has disproportionately affected racial/ethnic minorities, including children, in terms of infections, hospitalizations, and death (Lopez, Hart, & Katz, 2021; Van Dyke et al., 2021). Other sociodemographic risk factors such as household composition, socioeconomic status, limited English proficiency, housing type, and transportation are also associated with Covid-19 incidence and mortality (Karmakar, Lantz, & Tipireni, 2021).

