Measures: Participants will also be asked to complete the following measure immediately following the intervention:

COVID-19 Knowledge and Experience. COVID-19 knowledge and experience using items from the RADxUP common data elements and the PhenX Toolkit (Hamilton et al., 2011). Data to be collected include basic demographic data, COVID-19 knowledge and attitudes, health risk beliefs, vaccine confidence, COVID-19 related stigma/discrimination, COVID-19 trauma, and COVID-19 anxiety. Measures are attached.

Specific Secondary Outcome Measures:

- **PTSD as measured by the University of California Los Angeles (UCLA Brief COVID-19 Screen for Child/Adolescent Post Traumatic Stress Disorder (PTSD)**

- scores range from 0 to 4, higher scores indicate more symptoms of PTSD
- Time Frame: up to 6 months

- **COVID anxiety as measured by the Coronavirus Anxiety Scale**

- scores range from 0 to 4, higher scores indicate more symptoms of COVID specific anxiety
- Time Frame: up to 6 months

Part 1C

Overview: To assess the impact of the health education initiative on vaccination status and other health behaviors.

Consent: We are requesting a waiver of consent for the first section of Part C which is a few simple questions about the intervention. Informed consent will be obtained electronically via REDCap (detailed below), on paper, or verbally over the phone or in-person, with a study staff member reading aloud questions and recording the participant's responses. During the consent process, participants will be given ample time to review study procedures and provided contact information for the research team should they have questions.

Primary Outcome Measures: Participants will be asked to complete a few questions about the impact of the education session in the last 3 months. Measure is attached.

- **Number of caregivers who received COVID-19 vaccine**
 - unit of measure number of caregivers
 - Time Frame: up to 6 months
- **Number of children who received COVID-19 vaccine**
 - unit of measure number of children
 - Time Frame: up to 6 months
- **Health behaviors as measured by Health Behavior Questionnaire**
 - Scores range from 1 ("strongly disagree") to 5 ("strongly agree"), with higher scores indicating greater intent to engage in health behaviors to prevent COVID-19.
 - Time Frame: up to 6 months

If participants agree they will also be given the opportunity to complete the COVID-19 assessment battery offered in Part B for additional compensation:

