 - Scores range from 1 ("strongly disagree") to 5 ("strongly agree"), with higher scores indicating greater intent to engage in health behaviors to prevent COVID-19.
 - Time Frame: up to 6 months
- **COVID-19 Knowledge and Experience.** COVID-19 knowledge and experience using items from the RADxUP common data elements and the PhenX Toolkit (Hamilton et

al., 2011). Data to be collected include basic demographic data, COVID-19 knowledge and attitudes, health risk beliefs, vaccine confidence, COVID-19 related stigma/discrimination, COVID-19 trauma, and COVID-19 anxiety. Measures are attached.

Specific Secondary Outcome Measures:

- **PTSD as measured by the University of California Los Angeles (UCLA) Brief COVID-19 Screen for Child/Adolescent Post Traumatic Stress Disorder (PTSD)**
 - scores range from 0 to 4, higher scores indicate more symptoms of PTSD
 - Time Frame: up to 6 months
- **COVID anxiety as measured by the Coronavirus Anxiety Scale**
 - scores range from 0 to 4, higher scores indicate more symptoms of COVID specific anxiety
 - Time Frame: up to 6 months
-

Part 2B

Overview: Control participants will be invited to complete a follow-up survey that assesses their COVID-19 knowledge and experience approximately three months following the initial survey. The survey will be conducted through a secure online data collection method (e.g., REDCap or Qualtrics), on paper, or verbally over the phone or in-person, with a study staff member reading aloud questions and recording the participants' responses. If interested and eligible, participants will be given access to the online survey via a link sent by email, by scanning a QR code. If preferred, they will be given the option to complete the survey verbally over the phone or in-person, or to complete it on paper.

Informed Consent: Informed consent will be obtained electronically via REDCap (detailed below) or on paper. During the consent process, participants will be given ample time to review study procedures and provided contact information for the research team should they have questions.

Primary Outcome Measures: Participants will complete the following measures:

- **Number of caregivers who received COVID-19 vaccine**
 - unit of measure number of caregivers
 - Time Frame: up to 6 months
- **Number of children who received COVID-19 vaccine**
 - unit of measure number of children
 - Time Frame: up to 6 months
- **Health behaviors as measured by Health Behavior Questionnaire**

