Recruitment: Participants will be re-contacted via the information they provided during Part A and ask if they are still interested in participating. If so, they will be given the link to complete the consent and 3-month follow-up measures, or will be given the opportunity to complete paper forms in-person at study sites.

Compensation: Participants will receive \$30 payment for completing one measure and a \$25 payment for completing the rest of the 3-month post intervention measures if they choose to do so.

Control Participants

Part 2A

Recruitment: Participants will be recruited from the following schools: Fulford Elementary, Greynolds Park Elementary, North Miami Middle school, and North Miami Beach High; they may also be from “intervention schools,” (i.e., Arch Creek Elementary, Sabal Palm Elementary, JFK Middle, North Miami High, and Booker T. Washington High) but must not have participated in the intervention. Parents/guardians from each school will be recruited via flyers posted at their schools (see flyer attached), sent home via mailings, or posted on school websites; advertising at school events; word of mouth by school champions; and/or school messaging systems. Additionally, individuals who indicated interest in research on clinical consent forms may be contacted. The recruitment method will depend on acceptability to administrators and the school community.

Compensation: Participants will receive a \$50 payment for completing the questionnaires.

Part 2B

Recruitment:

Participants will be re-contacted via the information they provided during Part 2A and asked if they are still interested in participating. If so, they will be given the link to complete the consent and 3-month follow-up measures, or will be given the opportunity to complete paper forms in-person at study sites.

Compensation: Participants will receive a \$55 payment for completing the follow-up questionnaires.

15) Confidentiality

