We are requesting a waiver of consent for the first section of Part C which is a few simple questions about the intervention. For the second section of Part C, informed consent will be obtained from all participants via written/electronic signature along with consent for part 1B. Study staff will emphasize the voluntary nature of the study, the possible benefits and outcomes, alternatives to participation, confidentiality of participation, and the participant's right to refuse and/or withdraw from the study at any time. Consents will be available in English, Spanish, and Creole. Staff who speak these languages are part of our study team and will assist with questions as need be. All participants will have sufficient time to consider their participation.

Control Participants

Parts 2A and B

Informed consent will be obtained from all participants via written/electronic signature. Study staff will emphasize the voluntary nature of the study, the possible benefits and outcomes, alternatives to participation, confidentiality of participation, and the participant's right to refuse and/or withdraw from the study at any time. Consents will be available in English, Spanish, and Creole. Staff who speak these languages are part of our study team and will assist with questions as need be. All participants will have sufficient time to consider their participation.

19) Process to Document Consent in Writing

Intervention Participants

Part 1A

We are requesting a Waiver of Documentation of Consent for this portion of the study will be obtained as study procedures pose minimal risk and the waiver will not adversely affect the rights and welfare of the participants. Although participants will not provide written consent due to this waiver, they will be provided with information relevant to consent, including information about study procedures, potential risks/benefits of participation, voluntariness of the study, their right to withdraw, and contact information for the research team. Participants will indicate their consent by completing the evaluation form.

Part 1B

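### The 3-month vaccination and health-behavior outcomes are described as questions about the session for attenders but neutrally for controls, so a like-for-like comparison is not assured

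*Protocol*

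**What the plan says.** In Section 5, under Part 1C, the primary outcomes for attenders at three months open with "Participants will be asked to complete a few questions about the impact of the education session in the last 3 months". The protocol adds that the measure is attached. Three outcomes follow directly: number of caregivers vaccinated, number of children vaccinated, and the Health Behavior Questionnaire, scored 1 to 5 with higher scores meaning stronger intent.

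The consent paragraph of Part 1C requests a "waiver of consent for the first section of Part C which is a few simple questions about the intervention". Sections 18 and 19 repeat that description for Part 1C.

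For controls at three months, Part 2B in Section 5 lists the same three outcomes under a plain introduction: "Primary Outcome Measures: Participants will complete the following measures". It calls the occasion a "follow-up survey that assesses their COVID-19 knowledge and experience approximately three months following the initial survey". Part 2A requires that controls did not take part in the intervention.

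Section 2 states the purpose of Part 2B as "Comparing COVID-19 knowledge, experience, and health behaviors of participants in the health education initiative to controls, three months after the initiative".

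**The concern.** A comparison of health behaviors at three months needs the same question, over the same recall period, in both groups. Controls cannot be asked what a session they did not attend did for them. If the attender items are put in terms of the session and the control items are not, the two groups answer different questions under one outcome name.

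The outcomes are self-reported. A prompt that points to the session may lead attenders to report, or credit to it, more change than they otherwise would. Such a shift would favour the initiative. Because the framing would coincide exactly with group membership, no later adjustment could separate it from a true effect.

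**Working it through.** No arithmetic applies. The protocol states no figure on this point, and the supplied text gives no item wording or standard deviation from which a bias could be sized. The check is a comparison of the descriptions.

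| Feature | Attenders, Part 1C | Controls, Part 2B |
|---|---|---|
| Introduction to the primary outcomes | Impact of the session | Neutral list of measures |
| Description in the consent text | Questions about the intervention | No such description |
| Exposure to the session | Yes | None, by the Part 2A requirement |
| Outcomes listed | Caregiver vaccination, child vaccination, Health Behavior Questionnaire | Same three |
| Units, scale, time frame | Number of caregivers, number of children, 1 to 5, up to 6 months | Same |
| Item wording, order and recall period | On the attached form, not shown | Not shown |

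1. **Is it a single loose sentence?** No. The session-based description appears four times: in the outcome text of Part 1C, in its consent paragraph, and under Part 1C in Sections 18 and 19. In the last three places it describes the section for which a consent waiver is requested.
2. **Does it cover the primary outcomes?** As written, yes. The sentence stands under the primary-outcome label, and the three outcomes follow it directly.
3. **Is the comparison intended?** Yes. Objective 2B names health behaviors, and the three outcomes are labelled primary in both parts.
4. **Does the protocol say that both groups get the same neutral items?** No such statement was found. Matching names, units and scale are compatible with identical items but do not establish them.
5. **Which outcomes are most exposed?** The Health Behavior Questionnaire is an agreement scale of intent, so wording and context can readily move it. Whether a person was vaccinated is a matter of fact. It can be asked the same way of everyone and is less open to leading.

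**The case against.** The strongest reply is that the criticism rests on a form the reader cannot see. Part 1C's overview says that the part assesses the initiative's impact on vaccination and other behaviors. The opening sentence may simply repeat that purpose, and the waiver text may be shorthand for a short form. The definitions below the sentence do not mention the session: a vaccination count and an intent score are defined identically in Parts 1C and 2B. They also appear in Part 1A without any sentence about impact. This stands as a limit on what can be concluded. It does not remove the inconsistency, because the description recurs and the protocol does not say that the items are common to both groups.

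The reply is also right about the analysis. Section 7 describes the Part 1C surveys by school and names mixed models only for knowledge and vaccine confidence. Both come from a battery described in the same terms for both groups, so no named model is shown to be affected. The health-behavior comparison nevertheless remains a stated objective.

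A reader might infer several stronger points that the documents do not support:

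- **The outcomes are in fact not comparable, and answers are in fact led.** Without the items, neither can be asserted.
- **Payment pushes attenders towards favourable answers.** At three months attenders can receive $30 + $25 = $55 and controls receive $55. The $50 tied to attendance belongs to Part 1A.
- **Having staff read the questions aloud adds bias in one group.** It is offered to both groups.
- **The bias can be put in standard-deviation units.** Any such figure would only divide one assumed number by another.

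**Conclusion.** The point holds as a matter of description and assurance. The protocol describes the 3-month primary section as being about the session for attenders, and lists the same outcomes neutrally for unexposed controls. Comparability for the health-behavior part of objective 2B is therefore not assured. Any framing effect would probably favour the initiative, chiefly through the 1-to-5 intent score.

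Its size is unknown and cannot be derived from the protocol. The conclusion assumes that the form follows its description. If the attached form already uses common neutral items, only the protocol text is at fault. The change is still worth making, because it is cheap and because a framing effect, once in the data, could not be removed by analysis.

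**What to change.** State in Parts 1C and 2B that the vaccination and health-behavior items come first, in identical neutral wording, with the same recall period and no reference to the session. Place any questions on the session's perceived impact at the end of Part 1C, for attenders only, and report them as acceptability rather than as a primary outcome. Bring the Part 1C introduction and the waiver wording in Sections 5, 18 and 19 into line with this.

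The cost is rewording and reordering short forms, retranslation into Spanish and Creole, and an IRB amendment. No new study procedure is needed. If the forms already meet this standard, correcting the description is enough.

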COVID-19 Knowledge and Experience. COVID-19 knowledge and experience using items from the RADxUP common data elements and the PhenX Tookit (Hamilton et al., 2011). Data to be collected include basic demographic data, COVID-19 knowledge and attitudes, health risk beliefs, vaccine confidence, COVID-19 related stigma/discrimination, COVID-19 trauma, and COVID-19 anxiety. Measures are attached.

Specific Secondary Outcome Measures:

- **PTSD as measured by the University of California Los Angeles (UCLA) Brief COVID-19 Screen for Child/Adolescent Post Traumatic Stress Disorder (PTSD)**

- scores range from 0 to 4, higher scores indicate more symptoms of PTSD
- Time Frame: up to 6 months
- **COVID anxiety as measured by the Coronavirus Anxiety Scale**
 - scores range from 0 to 4, higher scores indicate more symptoms of COVID specific anxiety
 - Time Frame: up to 6 months

Control Participants

Part 2A

Overview: Control participants will be invited to complete a survey that assesses their COVID-19 knowledge and experience. The survey will be conducted through a secure online data collection method (e.g., REDCap or Qualtrics), paper, or verbally over the phone or in-person, with a study staff member reading aloud questions and recording the participant's responses. If interested and eligible, participants will be given access to the online survey via a link sent by email or by scanning a QR code. If preferred, they will be given the option to complete the survey verbally over the phone or in-person, or to complete it on paper. Control participants may be recruited from any of the study schools (i.e., intervention or control). They must not have participated in the intervention.

Informed Consent: Informed consent will be obtained electronically via REDCap (detailed below) or via paper forms. During the consent process, participants will be given ample time to review study procedures and provided contact information for the research team should they have questions.

Primary Outcome Measures: Participants will complete the following measures:

- **Number of caregivers who received COVID-19 vaccine**
 - unit of measure number of caregivers
 - Time Frame: up to 6 months
- **Number of children who received COVID-19 vaccine**
 - unit of measure number of children
 - Time Frame: up to 6 months
- **Health behaviors as measured by Health Behavior Questionnaire**

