Part 1C: Evaluating the impact of the health education initiative on vaccination rates and other health behaviors 3 months following the intervention. Three month post surveys will be summarized and described by school. Assessing COVID-19 knowledge and experience among caregivers of students in at-risk urban school settings 3 months post-intervention.

Part 2A & 2B: Mixed models will be used to examine change in knowledge over time (repeated measure) among participants who have participated in the education session, compared to those who haven't. Likewise, vaccine confidence will be analyzed with a mixed

model to examine change over time, compared to those who did not participate in the education session.

8) Risks to Subjects*

The potential risks in this study are minimal. It is possible some subjects may experience discomfort while responding to questions about COVID-19. However, we incorporated stakeholder feedback on most acceptable methods (i.e., culturally sensitive, addressing their concerns) to discuss COVID-19 testing, diagnosis, and vaccination with participants, to minimize discomfort.

9) Potential Benefits to Subjects*

Participants may gain knowledge about how to maintain health and safety during the era of COVID-19. However, some participants may experience no direct benefit.

10) Vulnerable Populations*

N/A

11) Setting

This study will take place at 9 Miami Dade County Public Schools served by the UM School Health Initiative:

- Intervention schools: Arch Creek Elementary, Sabal Palm Elementary, JFK Middle, North Miami High, and Booker T. Washington High.
- Control schools: Fulford Elementary, Greynolds Park Elementary, North Miami Middle school, and North Miami Beach High or those who did not participate in the intervention at “intervention schools”: Arch Creek Elementary, Sabal Palm Elementary, JFK Middle, North Miami High, and Booker T. Washington High.

12) Resources Available

Our research staff consists of personnel familiar with the protocol. Members of the research team have experience in patient outreach and follow up, conduct of clinical research, statistical analysis and methodology. Additionally, students could seek comprehensive medical services delivered by the School Health Initiative.

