Co-Investigator [name] is a Professor of Public Health Sciences and the Director of Public Health Education in the Department of Public Health Sciences at the University of Miami, Miller School of Medicine. She has over 21 years of experience in the design and implementation of multisite clinical trials, and in the efficient management and oversight of remote sites and demonstrated experience in the development and implementation of trials for Hispanics and Spanish speakers. [name] research career has been committed to improving practice through the implementation of clinical trials in real-world settings, and more recently in creating the local capacities that would allow the implementation of such trials. She will be responsible for monitoring the measurement and assessment protocols and will assist in manuscript preparation. She will work closely with our statistician to prepare routine reports on data collection and analyses.

13) Prior Approvals

Approval must also be obtained by the Miami Dade County Public Schools IRB prior to commencing this study.

14) Recruitment Methods

Intervention Participants

Part 1A

Recruitment: Participants will be recruited from the following schools: Arch Creek Elementary, Sabal Palm Elementary, JFK Middle, North Miami High, and Booker T. Washington High. Parents/guardians from each school will be recruited via flyers posted at their schools (see flyer attached), sent home via mailings, or posted on school websites; advertising at school events; word of mouth by school champions; and/or school messaging systems. Additionally, individuals who indicated interest in research on clinical consent forms may be contacted. The recruitment method will depend on acceptability to administrators and the school community.

Compensation: Participants will receive \$50 payment for attending the education session and completing the feedback forms.

Part 1B

Recruitment: Immediately following the health education initiative, participants will be invited to complete additional questionnaires. They will receive a flyer with information about questionnaires (see flyer attached) and links to complete them electronically, or will be given the opportunity to complete paper forms in-person at study sites.

Compensation: Participants will receive \$20 payment for completing the post-intervention measures.

Part 1C

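### The mixed model for Parts 2A and 2B targets change between two post-session surveys, so it does not estimate the between-group differences that objectives 2A and 2B ask for

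*Protocol*

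**What the plan says.** Section 2 (Objectives) gives the study's second purpose as a comparison of attenders with controls: Part 2A just after the initiative, Part 2B three months after it.

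Section 7 (Data Management, Part 2A & 2B) gives one combined analysis for the two parts. For knowledge: "Mixed models will be used to examine change in knowledge over time (repeated measure) among participants who have participated in the education session", compared with people who did not attend. For vaccine confidence it plans a mixed "model to examine change over time, compared to those who did not participate in the education session". It states no between-group comparison at either time point. Elsewhere Section 7 is descriptive; for Part 1C, "Three month post surveys will be summarized and described by school".

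The measurement times are set in Sections 5 and 14:

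- **Attenders, first battery (Part 1B).** Section 5: "Participants will also be asked to complete the following measure immediately following the intervention". Section 14 agrees: "Immediately following the health education initiative, participants will be invited to complete additional questionnaires". The Part 1A forms are also completed after the session.
- **Attenders, second battery (Part 1C, three months).** It is optional: "If participants agree they will also be given the opportunity to complete the COVID-19 assessment battery offered in Part B for additional compensation".
- **Controls, first survey (Part 2A).** "Control participants will be invited to complete a survey that assesses their COVID-19 knowledge and experience". It is not tied to the date of any session.
- **Controls, second survey (Part 2B).** About three months after their first.

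The protocol describes no pre-session measurement of knowledge or vaccine confidence.

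**The concern.** A comparison of change between arms measures an intervention's effect when the first measurement precedes the intervention. Here both attender measurements follow it. Whatever attenders learned is in both of their scores, so the contrast shows only how the gap between the groups moved over the following three months.

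Read as written, a session that raises knowledge and keeps it raised has an expected effect of zero, and one whose benefit partly wears off appears harmful, even though attenders outscore controls at both surveys. The Background section predicts increased knowledge, and the stated contrast could not show that increase. The control comparison is the protocol's second purpose rather than its first, but this is the only between-arm analysis that Section 7 states.

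**Working it through.** The protocol text at hand gives no sample size, effect size or power, so there is no planned figure to reproduce. The fault is algebraic; the numbers after step 2 only illustrate it.

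**1. The identity.** Let D1 and D2 be the attender-minus-control differences at the first survey and at three months. Objective 2A asks for D1 and objective 2B for D2. The between-arm difference in change is D2 - D1. Objective 2A concerns a single time point, so no change contrast can estimate it.

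**2. In terms of the session gain.** Let d be the gain, r the share kept at three months, c the share of controls who take up the whole gain between surveys (Section 5, Part 1A, allows a recording to be shared with the wider school community), and b any pre-existing or calendar-time difference common to both surveys. With a common time trend:

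- D1 = d + b
- D2 = (r - c)d + b
- change contrast = (r - 1)d - cd

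**3. Illustration.** Assumed, not from the protocol: n = 100 per arm, SD 1, d = 0.4, within-person correlation rho = 0.5, no clustering, b = 0, two-sided 5% normal test.

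- SE of the change contrast = sqrt(4(1 - rho)/n) = sqrt(4 × 0.5/100) = 0.141
- SE of a level difference = sqrt(2/n) = sqrt(2/100) = 0.141

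| Scenario | Change contrast (SD) | Significant | Power, first-survey difference | Power, 3-month difference |
|---|---|---|---|---|
| r = 1, c = 0 | 0 | 5.0% | 80.7% | 80.7% |
| r = 0.75, c = 0 | -0.10 | 10.9% | 80.7% | 56.4% |
| r = 0.5, c = 0 | -0.20 | 29.3% | 80.7% | 29.3% |
| r = 1.25, c = 0 | +0.10 | 10.9% | 80.7% | not computed |
| r = 1, c = 0.25 | -0.10 | 10.9% | 80.7% | 56.4% |

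In the last row D2 = (1 - 0.25) × 0.4 = 0.30, the same as for r = 0.75. The last two rows show that the contrast is not a pure measure of retention either: later gain and control exposure to the recording also enter it. A simulation of 10,000 runs agreed (5.3%, 11.1%, 28.1%, 10.7% and 11.0% significant, in row order).

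**4. Sensitivity.**

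- Sample size: at r = 0.5 the change contrast is significant 17% of the time with 50 per arm and 41% with 150. First-survey power is 52% and 93%.
- Correlation: at r = 0.5 and n = 100, rejection is 22% for rho = 0.3 and 45% for rho = 0.7. At r = 1 it stays at 5%.

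**5. Limits of the level differences.**

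- Selection: with d = 0 and b = 0.2, the difference is significant 29.3% of the time.
- Calendar time: a drift of 0.05 SD a month with controls surveyed three months later on average gives b = -3 × 0.05 = -0.15. The first-survey difference becomes 0.25 and power falls from 80.7% to 42.4%. The change contrast escapes this only if the drift is linear and both arms have the same interval between surveys.
- School clustering: Section 5 states "Control participants may be recruited from any of the study schools (i.e., intervention or control"), so the penalty depends on how far the arms share schools. Take 20 attenders in each of five schools and variance 2(1 - ICC)/100 + ICC × the sum over schools of (attender share - control share)². At ICC 0.05 the SE is 0.204 (power 50%) with controls only from the four control schools, 0.153 (74%) spread evenly over nine, and 0.138 (83%) from the attenders' own five. With so few schools, a t reference on 7 degrees of freedom lowers the 50% to about 40%.

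**The case against.** The strongest reply is that Section 7 is only two sentences on this point. It names no interaction term and never calls the change difference the session effect. A mixed model with arm, time and their interaction yields both level differences, and choosing contrasts from a stated model is usual SAP work. The Background also expresses interest in whether attitudes change after the intervention, which two post-session surveys could describe. And the replacement is itself open to selection and calendar bias, so a lower severity might do.

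Some of this stands. The model is sound and can be kept. The level differences are not clean effects. The numerical inputs are assumed, and the clustering figures have no bearing on the fault itself.

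The rest does not remove the problem. The protocol frames both outcomes as change over time against non-attenders and states no level comparison, so the text points to a quantity other than its own objectives; this is more than detail left for later. A SAP that followed the wording would report D2 - D1. The Background sentence is ambiguous and cannot serve objective 2A on any reading. Confounding of D1 and D2 limits how they are interpreted, but it does not turn their difference into an answer to the objectives.

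**Conclusion.** The concern holds and should be corrected before analysis. The only between-arm analysis in Section 7 targets D2 - D1, while the objectives ask for D1 and D2. That conclusion follows from the measurement schedule and needs no assumed numbers. The expected values of zero for a fully kept gain and below zero for a fading one assume a common time trend and no control uptake of the content between surveys. The percentages rest on the illustrative inputs above.

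The point is confined to knowledge and vaccine confidence, the two outcomes Section 7 models. The knowledge battery is headed a primary outcome only in the control lists; for attenders it appears under a general measures heading in Part 1B and is optional in Part 1C.

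**What to change.** Amend the Part 2A & 2B paragraph of Section 7:

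- Keep the mixed model with arm, time and arm-by-time terms.
- Name the between-arm differences at the first survey (2A) and at three months (2B) as the effect estimates for knowledge and vaccine confidence.
- Adjust for the demographics already collected and for survey calendar date, with a random intercept for school.
- Describe the arm-by-time term as the difference in post-session change (fading, later gain or control exposure to the recording), not as the session effect.
- Report the level differences as adjusted associations.

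**Cost.** One paragraph and no new questionnaire. It needs the completion date of each survey, which is assumed to be recorded because the protocol does not say so.

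**Remaining weakness.** Pre-existing differences may persist after adjustment, date adjustment helps only where the arms' survey dates overlap, and the three-month difference is exposed to selective return because the attenders' repeat battery is optional.

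**Optional, only if sessions remain.** Give the same items before the session, with a matched first survey in controls. Change from that baseline would capture the gain, still assuming parallel trends. It costs one more questionnaire per attender, the matched control survey, and moving Part 1B consent to before the session.
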